6.1.2 Administration

The recommended dose of Acalabrutinib is 100 mg (1 capsule) twice daily. Acalabrutinib should be swallowed whole with water at approximately the same time each day. Acalabrutinib can be taken with or without food. The capsule should not be chewed, dissolved, or opened.

6.2 Handling/storage/accountability

Acalabrutinib does not require any special storage conditions.

Only patients enrolled in the study may receive study treatment, and only authorised site staff may supply or administer study treatment. All study treatments must be stored in a secure, environmentally controlled, and monitored (manual or automated) area in accordance with the labelled storage conditions with access limited to the Investigator and authorised site staff.

The Investigator, Institution, or the head of the medical institution (where applicable) is responsible for study treatment accountability, reconciliation, and record maintenance (i.e., receipt, reconciliation, and final disposition records).

6.3 Measures to minimise bias: randomisation and blinding

Since the present study is an open-label phase IV trial, blinding and randomisation are not applicable.

6.4 Treatment compliance

Any change from the dosing schedule: dose interruptions, dose reductions, dose discontinuations should be recorded in the eCRF. There should be 100% compliance with the study medication. No drug interruptions and missed doses will be permitted in the study.

The Investigational Product Storage Manager(Investigator/delegate) is responsible for managing the IMP from receipt by the study site until the destruction or return of all unused IMP. The Investigator(s) is responsible for ensuring that the patient has returned all unused IMP.

6.5 Concomitant therapy

Any medication or vaccine, including over-the-counter or prescription medicines, vitamins, and/or herbal supplements that the patient is receiving at the time of enrolment or receives during the study must be recorded along with:

- Reason for use
- Dates of administration including start and end dates
- Dosage information including dose and frequency

Investigators may prescribe concomitant medications or treatments (e.g., acetaminophen, diphenhydramine) deemed necessary to provide adequate prophylactic or supportive care except for those medications identified as “excluded” as listed below:

- Any investigational anticancer therapy
- Any concurrent chemotherapy, radiotherapy, immunotherapy, biologic, or hormonal therapy for cancer treatment. Concurrent use of hormones for non-cancer-related conditions (e.g., insulin for diabetes and hormone replacement therapy) is acceptable.

NOTE: Local treatment of isolated lesions, excluding target lesions, for palliative intent is acceptable (e.g., by local surgery or radiotherapy).

- Strong inducers of CYP3A activity (e.g., Phenytoin, Rifampin, Carbamazepine).
- Strong CYP3A inhibitors (e.g., Clarithromycin, Telithromycin, Nefazodone, Itraconazole, Ketoconazole, Atazanavir, Darunavir, Indinavir, Lopinavir, Nelfinavir, Ritonavir, Saquinavir, Tipranavir).
- Proton pump inhibitors (e.g., Omeprazole, Esomeprazole, Lansoprazole, Dexlansoprazole, Rabeprazole, Or Pantoprazole).

NOTE: If treatment with an acid-reducing agent is required, consider using an antacid (e.g., calcium carbonate), or an H₂-receptor antagonist (e.g., Ranitidine).

6.5.1 Other concomitant treatment/s

Other medication/s other than that described above, which is/are considered necessary for the patient’s safety and wellbeing, may be given at the discretion of the Investigator and recorded in the appropriate sections of the electronic Case Report Form.

6.5.2 Rescue medication/s

Rescue medication/s, if required, will be provided by the Investigator as per the Standard of Care. The date and time of rescue medication administration, as well as the name and dosage regimen of the rescue medication, will be recorded

6.6 Dose modification

Dose escalation or reduction are recommended in the study. In addition, there are certain circumstances in which the study drug should be permanently discontinued (refer Appendix C and Section 7).

Acalabrutinib discontinuation will not be required for AEs that are clearly not attributed to study drug (such as an accident) or for laboratory abnormalities that are not deemed to be clinically significant.

7. DISCONTINUATION OF STUDY DRUG

7.1 Discontinuation of study treatment

Patients may be discontinued from the investigational product in the following situations:

- Patient decision. The patient is at any time free to discontinue treatment without prejudice to further treatment.
- Adverse Event that in the opinion of the Investigator or the Sponsor contraindicates further dosing
- Severe non-compliance to study protocol that, in the opinion of the Investigator or Sponsor, warrants withdrawal, e.g., refusal to adhere to scheduled visits etc.
- Any AE that meets criteria for discontinuation, as defined in Appendix D
- Initiation of alternative anticancer therapy including another investigational agent
- Disease progression as per the Investigator's clinical and imaging assessment.
- Pregnancy or intent to become pregnant.

If the patient is discontinued from the study, the patient will be followed up until the start of subsequent anti-cancer intervention or up to a duration of 28 days, whichever is earlier.

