1. PROTOCOL SUMMARY

1.1 Schedule of Activities (SoA)

Table 1: Schedule of Activities (SoA)

Study Phase	Screening Phase	Treatment Phase ^a		Follow-up Phase
Cycle		Cycles 1-6	EOT	EOS
Visit No.	1	2-7 (Day 1 of each cycle)	8	
Study Days	-6 to 0	1-168 (28 days per cycle)	170	28 days post-EOT
Screening/Enrolment visit				
Informed consent ^s	X			
Eligibility Criteria	X			
Demographics/ Review medical history	X			
ECOG Performance Status	X	X	X	
General Physical examination ^b	X	Symptom-directed physical examination only		
Concomitant medication recording	Continuous from the time of ICF until 28 days after the last Acalabrutinib dose in the treatment phase.			
Study Drug Administration				
Acalabrutinib dosing		The recommended dose is Acalabrutinib 100 mg capsules BID, starting on Day 1 Cycle 1, until disease progression or unacceptable toxicity. Each cycle of treatment is 28 days.		
Disease Evaluations (Disease characteristics will be performed as per routine clinical practice)				
Baseline Disease Characteristics	X			
Safety Evaluations (baseline and each treatment visit) [*]				
Physical examination ^b	X	Symptom-directed physical examination only		
Vital parameters ^c	X	X	X	
Adverse event monitoring	Continuous from the time of ICF until 28 days after last study dose of Acalabrutinib.			

Study Phase	Screening Phase	Treatment Phase ^a		Follow-up Phase
Cycle		Cycles 1-6	EOT	EOS
Visit No.	1	2-7 (Day 1 of each cycle)	8	
Study Days	-6 to 0	1-168 (28 days per cycle)	170	28 days post-EOT
12-lead ECG	X	X	X	
Lymph node biopsy ^d	X			
Next-generation sequencing (NGS)-CLL panel ^e	X			
Haematology ^f & Biochemistry ^g	X	X	X	
Urinalysis ^h	X	X	X	
Pregnancy Test ⁱ	X	X	X	
Chest X-ray ^j	X	X	X	
Efficacy Evaluations (once in 3 months)				
CT/MRI ^k	X	X	X	
EORTC QLQ-C30 Questionnaire	X	X	X	

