4.1.2 Treatment Phase (Visit 2 To 7)

The Treatment Phase will start from Cycle 1, Day 1 to Cycle 6, Day 28, or until study drug discontinuation due to either disease progression, unacceptable toxicity; or other reasons, whichever occurs earlier. Each cycle of treatment is defined as 28 days of twice-daily Acalabrutinib treatment.

Details of the procedures performed during the Treatment Phase are outlined in the Schedule of Activity table. Patients will be closely monitored for adverse events and other safety evaluations, including laboratory investigations, concomitant medications etc. as provided in SoA table. If disease progression is diagnosed before Day 168, then the patient will discontinue the study drug. The End-of-Treatment Visit evaluations will be completed on the day of progression and patient will enter the safety Follow-up Phase.

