4.1.4 Follow-Up Phase (End-Of-Study)

The Follow-up Phase will begin once a patient discontinues study drug or completes the Treatment Phase. The follow-up phase will continue until 28 days after last dose, loss to follow up, withdrawal of consent for study participation, or end of the study, whichever occurs earlier. A follow-up will be conducted 28 days after the EOT visit via a phone call. This will be considered as End-of-Study Visit. Every effort should be made to conduct the End-of-Study Visit.

Patients who are observed to receive clinical benefit from Acalabrutinib after completion of treatment phase, may continue to receive Acalabrutinib, if in the opinion of their treating physician they are continuing to derive clinical benefit from continued treatment or have not progressed clinically. The details on “Post-Trial Access” are provided in section 1.2.

For details on treatments given during the study, refer Section 6.1 Treatments Administered.

For details on what is included in the efficacy and safety endpoints, refer Section 3 and 8.

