8.2.2 Time period and frequency for collecting AE and SAE information

Adverse events and SAEs will be collected from the time of signature of informed consent, throughout the treatment period (168 days), End of study visit (Day 170) and including the follow-up period (28 days after the last dose of study drug) in patients who discontinue before 168 days.

If a patient discontinues from study drug for reasons other than disease progression, drug-related SAEs must be captured until the patient is initiated on an alternate intervention or up to 28 days, whichever is earlier.

All SAEs will be recorded and reported to the Sponsor or designee within 24 hours, as indicated in Appendix B. The Investigator will submit any updated SAE data to the Sponsor within 24 hours of it being available.

Investigators are not obligated to actively seek AE or SAE in former study patients. However, if the Investigator learns of any SAE, including death, at any time after a patient's last visit and he/she considers the event to be reasonably related to the study treatment or study participation, the Investigator may notify the Sponsor.

The method of recording, evaluating, and assessing causality of AE and SAE and the procedures for completing and transmitting SAE reports are provided in Appendix B.

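### Section 7.1 and the second paragraph of 8.2.2 end follow-up at the next anticancer therapy, while the SoA, 4.1.4 and the first paragraph of 8.2.2 run to 28 days after last dose

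*Protocol*

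**What the plan says.** Two places in the protocol cut follow-up at new therapy.

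- Section 7.1 closes with a sentence on patients discontinued from the study, which reads in part: "the patient will be followed up until the start of subsequent anti-cancer intervention or up to a duration of 28 days, whichever is earlier". It does not say from which day the 28 days run. The reasons for stopping listed just above it include progression and "Initiation of alternative anticancer therapy including another investigational agent".
- Section 8.2.2, second paragraph, covers patients who stop drug for reasons other than progression: "drug-related SAEs must be captured until the patient is initiated on an alternate intervention or up to 28 days, whichever is earlier".

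Three places run to 28 days after last dose and do not mention new therapy.

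- The SoA row for adverse event monitoring: "Continuous from the time of ICF until 28 days after last study dose of Acalabrutinib". SAP Section 2.2.5 repeats this row.
- Section 4.1.4: "The follow-up phase will continue until 28 days after last dose, loss to follow up, withdrawal of consent for study participation", or the end of the study, whichever is first. Progressors reach this phase through Section 4.1.2: "The End-of-Treatment Visit evaluations will be completed on the day of progression and patient will enter the safety Follow-up Phase".
- Section 8.2.2, first paragraph, which collects all AEs and SAEs, "including the follow-up period (28 days after the last dose of study drug) in patients who discontinue before 168 days".

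SAP Section 6.3.1 summarises AEs, SAEs and AESIs as frequencies and percentages. It sets no rule for events that begin after a new anticancer therapy, and Table 14.3.1 has no split on that basis.

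**The concern.** AEs and SAEs are the primary outcome. A patient who moves to another therapy soon after the last dose of acalabrutinib may be followed to the day of the switch at one site and to day 28 at another, with each site able to cite the protocol. The two patients then count equally in the same percentage.

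The shorter rule can lose late acalabrutinib events. The longer rule can bring in events caused by the next drug. Either could be defended if it were chosen and stated, but here both stand. Deaths are touched as well, because Section 8.2.7 ties their reporting to the protocol-defined follow-up period.

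**Working it through.** **1. The rules side by side**

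| Place | Who | What | Ends at |
|---|---|---|---|
| SoA, AE row | all | AEs | 28 days after last dose |
| 4.1.4 | all who stop or complete | follow-up phase | 28 days after last dose, loss, consent withdrawal or end of study |
| 8.2.2, para 1 | stopped before day 168 | all AEs and SAEs | 28 days after last dose |
| 8.2.2, para 2 | stopped, not for progression | drug-related SAEs | new therapy or 28 days, the earlier |
| 7.1, last sentence | discontinued from the study | follow-up | new therapy or 28 days, the earlier |

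For a progressor, 8.2.2 is clear and 7.1 stands against the rest. For other early stops, 8.2.2 itself carries both rules for drug-related SAEs.

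**2. Days lost.** If new therapy starts on day k after last dose, and the 28 days in 7.1 are also counted from last dose, the shorter rule drops 28 − k days: 21 (75%) at k = 7, 14 (50%) at k = 14, 7 (25%) at k = 21.

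**3. Weight of one patient.** Protocol Table 8 gives Clopper-Pearson 95% limits. Recomputed from beta quantiles, all 43 filled cells agree to within 0.005 percentage points. One extra patient with an event then means:

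- All patients: 1/100 = 1.0 point. For example, 3/100 (0.62% to 8.52%) becomes 4/100 (1.10% to 9.93%).
- CLL/SLL: 1/90 = 1.1 points. 3/90 (0.69% to 9.43%) becomes 4/90 (1.22% to 10.99%).
- MCL: 1/10 = 10 points. 0/10 (0% to 30.85%) becomes 1/10 (0.25% to 44.50%).

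**4. How many patients.** The documents give no number of switchers, time to next therapy or SAE risk, so every input here is assumed: 4 to 10 switchers, new therapy on day 7 to 21, a chance p of 10% to 30% of an SAE within the 28 days, 50% to 100% of affected patients with no earlier SAE, and all sites following 7.1. With a constant hazard, the chance that the first post-dose SAE falls after day k is (1 − p)^(k/28) − (1 − p).

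| k | p = 0.1 | p = 0.2 | p = 0.3 |
|---|---|---|---|
| 7 | 0.074 | 0.146 | 0.215 |
| 14 | 0.049 | 0.094 | 0.137 |
| 21 | 0.024 | 0.046 | 0.065 |

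- Low: 4 × 0.024 × 0.5 = 0.05 patients missed.
- Middle: 5 × 0.094 × (0.5 to 1.0) = 0.24 to 0.47.
- High: 10 × 0.215 × 1.0 = 2.1.

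A looser count takes any one type of AE, with 5 to 20 switchers and 10% to 30% having it only after the switch. It gives 5 × 0.1 = 0.5 to 20 × 0.3 = 6 patients. The top end needs 20 of 100 patients to switch within 28 days.

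**The case against.** The strongest reply is that the documents do indicate which window applies. Section 7.2 refers the reader to the SoA for what to collect at discontinuation and follow-up. Section 8 says the SoA summarises procedures and timing, and calls adherence to it essential. The SoA row has no stop at new therapy, and the SAP copies it. That stands: a reader might infer that sites are left with no direction, and the text does not support this. But a pointer to the SoA does not cancel two sentences that say something else.

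The reach of 7.1 is also open to argument. The sentence speaks of patients discontinued from the study and of follow-up, not of AE collection. Applying it to everyone who stops drug is an inference from the section it closes. The inference is reasonable, since withdrawal from the study has its own Section 7.2, where the day of withdrawal ends the study phase and so leaves no room for up to 28 days. It remains an inference.

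A reader might go further and say that patients stopped because another therapy was begun get 0 days of follow-up. That is one reading only. The therapy called subsequent in 7.1 need not be the one that caused the stop, and the second paragraph of 8.2.2 can be read as a minimum that leaves the first paragraph in force.

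A reader might also say that the SAP outputs cannot tell acalabrutinib events from those of the next drug. They can, in part. Table 14.3.1 has causality rows, Listing 16.2.12.2 carries SAE causality to other medication, and Listings 16.2.11.1 and 16.2.20 hold AE and medication start dates. What is absent is a planned split.

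Finally, a late event in a patient who has already had an AE does not move the any-AE row, and no hypothesis is tested. Both points are correct and limit the size.

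**Conclusion.** The conflict is real and should be removed. Section 7.1, and the second paragraph of 8.2.2 within its narrower scope, set a cut-off that the SoA, 4.1.4 and the first paragraph of 8.2.2 do not have. Where a site applies it, late primary-outcome events go unrecorded in patients who switch within 28 days, and no later analysis can recover them.

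The loss is probably small: under half a patient with an SAE in the middle case, and about two only if every assumption in that SAE calculation is at its extreme and all sites follow 7.1. It would be easiest to see in the MCL column, although a 10-point step there is true of any single patient among 10. Nothing here puts the trial's overall safety conclusion in doubt. The conflict rests on the text alone; the size rests on assumptions that the documents cannot confirm.

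**What to change.** **Protocol.** Amend the last sentence of 7.1 and the second paragraph of 8.2.2 so that all AEs, SAEs and deaths are collected to 28 days after the last treatment-phase dose, whatever the reason for stopping and whether or not new therapy has started. The treatment-phase wording matters because patients may continue drug under post-trial access without active AE monitoring. The SoA concomitant-medication row already uses it: "Continuous from the time of ICF until 28 days after the last Acalabrutinib dose in the treatment phase".

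**SAP 6.3.1.** Flag events that start on or after the first dose of a new anticancer therapy, using the AE and medication start dates already collected, and show incidence with and without them. This makes the trade-off between lost and added events visible. The start of the AE counting period is not at issue and needs no change.

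**Cost.** Two protocol sentences, which need ethics committee approval under Appendix A 1, and one derived flag. The follow-up call and medication recording are already planned, so no visit is added. If the amendment comes too late to change collection, the SAP flag is still worth adding.

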7.2 Withdrawal from the study

A patient may withdraw from the study (e.g., withdraw consent), at any time at his/her own request, without prejudice to further treatment.

A patient who considers withdrawing from the study must be informed by the Investigator that the day of withdrawal will be considered as the end of the study phase for the patient. However, the patient will still have the provision of spontaneous AE reporting.

If the patient withdraws consent for disclosure of future information, the Sponsor may retain and continue to use any data collected before such a withdrawal of consent.

If a patient withdraws from the study, he/she may request the destruction of any samples taken, and the Investigator must document this in the site study records.

A patient who withdraws consent will always be asked about the reason(s) and the presence of any adverse events (AE). The Investigator will follow up with patients, as medically indicated.

AstraZeneca or its delegate will request Investigators to collect information on patients' vital status (dead or alive; date of death when applicable) at the end of the study from publicly available sources, in accordance with local regulations. Knowledge of the vital status of all patients at the end of the study is crucial for the integrity of the study.

Refer SoA, Table 1, for data to be collected at the time of study discontinuation and follow-up and for any further evaluations that need to be completed.

8. STUDY ASSESSMENTS AND PROCEDURES

Study procedures and their timing are summarised in the SoA, Table 1.

Written informed consent for participation in the study must be obtained before performing any study specific screening tests or evaluations. Informed Consent Forms for enrolled patients and for patients who are not subsequently enrolled will be maintained at the study site.

Documented evidence of CLL/SLL and MCL positive status from previous testing is acceptable, otherwise it has to be assessed at a local laboratory that is experienced/certified in CLL/SLL and MCL testing using an accurate and validated assay.

Women with child bearing potential and male patients with partners of child bearing potential who are sexually active will have to agree to use a highly effective, non-hormonal form of contraception (such as surgical sterilization) or two effective forms of non-hormonal contraception (such as a barrier method of contraception in conjunction with spermicidal jelly) during and for at least 6-months post-study treatment.

Screening tests and evaluations will be performed within 7 days prior to the first study medication administration (dosing). CT or MRI scans will be performed prior to the first study medication administration (dosing). CT or MRI scans are applicable for the patients with lymphadenopathy or organomegaly. Patients with abnormalities of blood parameters without any lymphadenopathy or organomegaly will not undergo CT or MRI scans. Patients who will be undergoing CT, should have baseline and every 3-months reports.

All screening evaluations must be completed and reviewed to confirm that patients meet all eligibility criteria before enrolment. The investigator will maintain a screening log to record details of all patients screened and to confirm eligibility or record reasons for screening failure, as applicable.

The safety assessments during the treatment visit will be performed at the start of each treatment cycle. However, efficacy assessments will be scheduled every three months during the study treatment period and EOT.

The Investigator will ensure that data are recorded in the eCRF.

The Investigator ensures the accuracy, completeness for eCRFs that includes: timeliness of the data recorded and query resolution according to the Clinical Study Agreement. The Investigator will sign the completed eCRFs.

Immediate safety concerns should be immediately discussed with the Sponsor upon occurrence or awareness to determine if the patient should continue or discontinue study treatment.

Adherence to the study design requirements, including those specified in the SoA, is essential and required for study conduct.

All screening evaluations must be completed and reviewed to confirm that potential patients meet all eligibility criteria. The Investigator will maintain a screening log to record details of all patients screened, confirm their eligibility for the trial, or record reasons for screening failure, as applicable.

Procedures conducted as part of the patient's routine clinical management (e.g., blood count) and obtained before signing of the ICF may be utilised for screening or baseline purposes provided the procedures meet the protocol-specified criteria and were performed within the time frame defined in the SoA.

The maximum amount of blood collected from each patient will not exceed approximately 10 mL/visit. Repeat or unscheduled samples may be taken for safety reasons or for technical issues with the samples

